13.2 Sample Size

Sample size is based on testing our primary endpoint using Simon's optimal two stage design with a type I error of 5% and power of 80%.³⁰ Our null hypothesis is that the response is $\leq 5\%$ (as all will be progressing on anti-PD1 therapy) and our alternative hypothesis is that response is $\geq 20\%$. If the treatment is truly not effective, there is a 5% chance of concluding that the drug is effective while if the treatment is truly effective, there is a 20% chance of concluding that it is not effective. Up to 10 patients will be enrolled per year.

13.3 Statistical Analysis

The primary endpoint of response will be estimated with a simple proportion and a 95% confidence interval. The secondary endpoints of survival and progression-free survival will be estimated with Kaplan-Meier curves. Disease control will be assessed with descriptive statistics and plots such as medians, ranges, interquartile ranges and box-plots. Toxicities will be assessed with descriptive statistics and plots such as simple proportions and bar graphs. Quality of life scores, as measured by PROMIS, will be evaluated descriptively at baseline, every 3 weeks during and at the final visit using medians, ranges, interquartile ranges and boxplots to look for trends in various areas measured by PROMIS. Analysis of correlative objectives will involve assessment of associations of baseline measurements of five biomarkers from tumor tissue and clinical outcome. Biomarkers will be evaluated by evaluation of quartiles with subsequent dichotomization and then comparison by response using a Chi-square test or Fisher's exact test depending on sample size. Evaluation of biomarkers is primarily descriptive and will be used in the planning of future studies both for selection criteria and validation. Six biomarkers from blood will similarly be assessed; however, these measurements will be assessed at individual post-treatment time-points as well. If warranted, repeated measures analyses may be used to look at measurements over time. There is currently no plan to demonstrate that the biomarkers could be used as surrogate endpoints but rather if associations exist for future evaluation.

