13.1 Study Design, Objectives and Endpoints

The goal of this phase II study is to estimate the probability of response after treatment of exemestane in post-menopausal women with advanced non-small cell lung cancer progressing while on immune checkpoint blockade. The primary endpoint of treatment response will be assessed at 6 weeks after the start of treatment using RECIST criteria. Secondary endpoints include the proportion of toxicities through 30 days after the last dose or start of new treatment as described in Section 10.2.2, disease-control as measured by response duration, progression-free and overall survival through 12 months from study enrollment and quality of life scores as measured by PROMIS-29 at baseline, every 3 weeks during treatment and at the end of treatment visit. The primary endpoint of response will be evaluated using a two-stage design.

Stage 1 will enroll 10 patients. If 2 or more patients have an objective response after completion of stage 1, an additional 19 patients will be enrolled in stage 2 for a total of 29 patients. If the total number of patients responding is 4 or greater, the treatment will be considered worthy of further investigation.

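### Section 13.3 analyses response as a fixed sample: a design-based estimate and an interval that match the two-stage test should be added beside the simple proportion

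*Combined protocol and SAP*

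**What the plan says.** Section 13.3 gives the whole primary analysis in one sentence: "The primary endpoint of response will be estimated with a simple proportion and a 95% confidence interval". It names no interval method, does not mention the two-stage sampling and does not tie the interval to the success rule.

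Section 13.1 sets out the sampling. "Stage 1 will enroll 10 patients"; the trial goes on to 29 only "If 2 or more patients have an objective response after completion of stage 1". Success is a count: "If the total number of patients responding is 4 or greater, the treatment will be considered worthy of further investigation". Section 13.2 sizes the trial "using Simon's optimal two stage design with a type I error of 5% and power of 80" per cent, with a null response rate of at most 5% and an alternative of at least 20%. Sections 1.1 and 13.1 both describe the aim as estimating response.

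**The concern.** A trial that can stop at 10 patients because responses are few does not yield a fixed binomial sample. Unlucky starts are frozen at a low proportion, while lucky starts are diluted by 19 more patients, so the simple proportion is not unbiased. That matters more than usual here because estimation is the stated objective.

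The interval and the decision rule also answer different questions. The count rule is in effect a one-sided 5% test under two-stage sampling. The planned interval is two-sided 95% and, as written, fixed-sample. At the lowest successful result, 4/29, the report could call exemestane worthy of further study beside an interval that contains the null rate. Because no method is named, whether that happens could turn on a choice made after the data are seen.

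**Working it through.** **Inputs.** From 13.1: Stage 1 n = 10, continue at 2 or more, total 29, success at 4 or more. From 13.2: null 5%, alternative 20%, type I error 5%, power 80%. Assumptions: the test is one-sided (inferred from the form of the null), and exactly 10 or 29 evaluable patients are analysed, with no toxicity stop.

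**The plan's own figures first.** Let X ~ Bin(10, p) and Y ~ Bin(19, p), and let c be the number of Stage 1 responses needed to continue. P(success) = P(X ≥ c and X + Y ≥ 4).

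- c = 2 (printed): 2.59% at p = 5% and 59.6% at p = 20%. The stated power is not reproduced.
- c = 1: 4.68% and 80.1%. A search for Simon's optimal design at the stated error rates returns this one (stop at 0/10, fail at 3/29 or fewer).

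The adjusted results depend on c, so both are shown.

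**Bias of the simple proportion, p = 20%.**

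- c = 2: P(stop) = 0.3758. The stopped part contributes P(X = 1) × 1/10 = 0.2684 × 0.1 = 0.0268. The continued part has mean 0.2267 and contributes 0.6242 × 0.2267 = 0.1415. Total 0.1683, bias −3.2 points.
- c = 1: stopping means 0/10 and contributes nothing. 0.8926 × 0.2083 = 0.1859, bias −1.4 points.

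At p = 10% the mean is 7.7% under either rule (bias −2.3 points). Restricted to trials declared positive at p = 20%, the mean is 23.3% (c = 2) or 22.2% (c = 1), which is above the truth.

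**UMVUE at 4/29.** Formula: Σ C(9, x−1)·C(19, 4−x) / Σ C(10, x)·C(19, 4−x), summed over x from c to 4.

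- c = 2: (1539 + 684 + 84) / (7695 + 2280 + 210) = 2307/10185 = 22.7%.
- c = 1: (969 + 2307) / (9690 + 10185) = 3276/19875 = 16.5%.

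The simple proportion is 4/29 = 13.8%.

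**Intervals at 4/29.** For the two-stage exact interval under stage-wise ordering, every Stage 1 stop ranks below every Stage 2 result. The lower limit solves P(continue and total ≥ 4) = α/2, and the upper limit solves P(stop, or total ≤ 4) = α/2.

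| Interval at 4/29 | 95% | 90% |
|---|---|---|
| Exact (Clopper-Pearson), fixed sample | 3.9% to 31.7% | 4.85% to 28.8% |
| Wilson, fixed sample | 5.5% to 30.6% | 6.3% to 27.4% |
| Two-stage exact, c = 2 | 4.95% to 44.6% | 6.2% to 39.6% |
| Two-stage exact, c = 1 | 4.1% to 34.3% | 5.1% to 30.8% |

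Wald, mid-P, Jeffreys and Agresti-Coull 95% intervals also include 5% (lower limits 1.2%, 4.5%, 4.8% and 4.9%). The fixed-sample one-sided p-value at 5% is 0.0548. The two-stage p-value is 0.0259 (c = 2) or 0.0468 (c = 1), so only the two-stage calculation agrees with the count rule at the 5% level.

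**How often this arises.** Exactly 4/29 makes up 0.0616/0.5963 = 10% (c = 2) or 0.1201/0.8011 = 15% (c = 1) of positive trials at a true 20%. At a true 10% the shares are 0.0731/0.1747 = 42% and 0.1427/0.2889 = 49%. At 5/29 every ordinary 95% interval listed above except Wald excludes 5%.

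**The case against.** The strongest reply is that no decision depends on this. Success is the count, no section requires the interval to exclude 5%, and the objective in 1.1 is only a preliminary estimate. The ordinary exact interval keeps its coverage under this design (97.6% to 99.2% for true rates from 5% to 30%). All of that stands, and it sets the severity.

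Three stronger readings are tempting, and the documents do not support them.

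- A reader might infer that ignoring the futility stop is what puts 5% inside the interval at 4/29. A two-stage 95% interval includes 5% as well. The main cause is the tail area.
- A reader might infer that only a two-stage interval can agree with the decision. Section 13.3 names no method. Ordinary Wilson excludes 5% at 95%, and at 90% so do Jeffreys, Agresti-Coull and mid-P (lower limits 5.9%, 5.9% and 5.6%). The two-stage interval is preferable because it uses the test's own sampling distribution.
- A reader might infer that the plan understates the rate carried into a next study. A next study follows a positive trial, where the simple proportion averages high.

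The objection also limits the remedy. Among positive trials at a true 20% the UMVUE averages 28.0% (c = 2) or 23.4% (c = 1), further above the truth than the simple proportion. Under the printed rule its root mean squared error is larger at rates of 5% to 20% (at 20%, 10.9 against 10.2 points). It should not displace the simple proportion.

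**Conclusion.** The point holds as a minor to moderate reporting matter. Section 13.3 specifies a fixed-sample estimate and an unnamed interval for two-stage data. The low bias, −1.4 to −3.2 points at a true 20%, is an average over all outcomes, including trials stopped at Stage 1. At 4/29 most ordinary 95% intervals, and the ordinary exact 90% interval, contain the rate that the decision rule rejects. The two-stage exact 90% interval does not, under either Stage 1 rule.

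This rests on reading the test as one-sided and on the nominal sample sizes. Which of the paired figures applies cannot be settled until the Stage 1 rule (Synopsis, Section 3, Section 13.1) is reconciled with the type I error and power in 13.2. That is a separate and larger issue.

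**What to change.** Reconcile the Stage 1 rule with 13.2 first. Then extend the sentence in 13.3 along these lines:

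> Response will be reported as the observed proportion and as the UMVUE for the two-stage design, with a one-sided p-value against 5% and a two-sided 90% exact confidence interval, both from the two-stage sampling distribution under stage-wise ordering. A 95% interval by the same method may be shown beside it; at 4 of 29 it can include 5%.

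The cost is a sentence or two in 13.3 and a few lines of code; sample size and decision rule stay as they are. There are two downsides to accept openly. The interval that matches the test is 90%, not 95%. Readers will also see two estimates that can differ noticeably (13.8% against 22.7% or 16.5% at 4/29), so the report should say that the UMVUE is unbiased over all outcomes and not among positive trials.

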FDA	Food and Drug Administration
ICB	immune checkpoint blockade
IRB	Institutional Review Board
MCC	Masonic Cancer Center
MDSC	myeloid derived suppressor cells
MNCCTN	Minnesota Cancer Clinical Trials Network
NSCLC	non-small cell lung cancer
OnCore	Online Enterprise Research Management Environment
OS	overall survival
PD	progressive disease
PFS	progression free survival
PR	partial response
RECIST	Response Evaluation Criteria in Solid Tumors
SAE	serious adverse event
SD	stable disease
SOC	standard of care

Synopsis

Phase II Trial of Exemestane in Previously Treated Post-Menopausal Women with Advanced Non-Small Cell Lung Cancer

Study Design:	
This is a phase II therapeutic study of adding exemestane therapy in post-menopausal women with advanced non-small cell lung cancer (NSCLC) who are progressing while on treatment with an immune checkpoint blockade antibody (pembrolizumab, atezolizumab, or nivolumab).
 
Enrollment will use a two-stage design. Stage 1 will enroll 10 patients. If at least 2 objective responses are observed at the first disease re-evaluation after beginning oral exemestane, Stage 2 will be activated. In Stage 2, an additional 19 patients will be enrolled for a total of 29 patients. If 4 or more objective responses are observed in the 29 patients, exemestane will be deemed worthy of further investigation in this population.

Primary Objective:	To determine a preliminary estimate of response of daily oral exemestane for the treatment of previously treated, advanced non-small cell lung cancer (NSCLC) in post-menopausal women receiving and progressing on immune checkpoint blockade (ICB) therapy.
Secondary Objectives:	
To determine the toxicity profile of daily exemestane in combination with immune checkpoint blockade therapy in this patient population.To estimate the disease control rate, progression-free survival (PFS), and overall survival (OS) of exemestane in this patient population through 1 year from study enrollment.To estimate quality of life during treatment and for 1 month after discontinuation.
Correlative Objectives:	
To conduct an exploratory biomarker correlative study of clinical outcome utilizing archived tumor tissue and serum collected at baseline and serially during therapy.To examine biomarkers in tissue post-treatment at the time of re-biopsy, if performed.To examine serum biomarkers of the peripheral immune response after aromatase inhibition.

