1.2 Secondary Objectives

- To determine the toxicity profile of daily exemestane in combination with immune checkpoint blockade therapy in this patient population.
- To estimate the disease control rate, progression-free survival (PFS), and overall survival (OS) of exemestane for up to 1 year from study enrollment in post-menopausal women with previously treated advanced NSCLC.
- To estimate quality of life during study treatment and for one month following discontinuation of study treatment.

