6.5 Duration of Study Participation

Direct study participation stops with the end of treatment visit; however all patients are followed for 1 year from the start of study treatment or until death, whichever is shorter.

Patients who discontinue treatment due to disease progression are followed for survival only (medical record review, local MD or patient contact) for 1 year from study treatment start.

Patients who discontinue treatment in the absence of disease progression are followed for disease response per standard of care until disease progression or the start of a new treatment, whichever is shorter and then for survival only for 1 year from study treatment start.

By 1 year from treatment start, all patients should have a last known date alive or a death date with cause recorded in OnCore, as well as, an initial date for disease progression in association with exemestane treatment.

7 Exemestane Drug Information

Names: exemestane, AROMASIN®, 6-Methyleneandrosta-1,4-diene-3,17-dione

Category: Aromatase Inhibitors

Indications: 1) For the treatment of advanced breast cancer in postmenopausal women whose disease has progressed following tamoxifen therapy and 2) adjuvant treatment of postmenopausal women with estrogen-receptor positive early breast cancer who have received two to three years of tamoxifen and are switched to exemestane for completion of a total of five consecutive years of adjuvant hormonal therapy.

Pharmacology: Aromatase is an enzyme that converts hormones to estrogen in the body's adrenal glands. The aromatase inhibitors (AIs) are drugs that reduce estrogen levels by blocking the action of aromatase in the adrenal glands. The selective AIs (SAIs) selectively reduce levels of estrogen without interfering with levels of other

steroid hormones that are produced by the adrenal gland. Drugs in this class include anastrozole (Arimidex™), letrozole (Femara™) and exemestane (Aromasin™)

Availability: For the purposes of this study a commercial formulation of Aromasin will be provided by the manufacturer, Pfizer. The study specific drug reorder form is attached in OnCore under this study. It is recommended that a drug inventory sufficient to treat study subjects for approximately four (4) weeks be maintained while waiting for additional ordered supplies.

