12.2 Secondary Endpoints

Toxicity will be assessed from the 1st dose of exemestane through 30 days after the last dose, or the start of a new anti-cancer treatment, whichever is earlier. Toxicity severity will be graded using the Common Toxicity Criteria for Adverse Events (CTCAE) version 4. Attribution and expectedness will be assigned per the definitions found in Section 10.1.

Response duration, progression-free survival and survival will be assessed until 1 year after study enrollment based on the definitions found in RECIST 1.1 (Appendix II).

Quality of life will be assessed by use of PROMIS-29 at baseline, every 3 weeks while on study drug and at the end of treatment visit.

13 Statistical Considerations

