Any	Any	Yes	PD	

* See RECIST 1.1 manuscript for further details on what is evidence of a new lesion.
 ** Only for non-randomized trials with response as primary endpoint.
 *** In exceptional circumstances, unequivocal progression in non-target lesions may be accepted as disease progression.

Note: Patients with a global deterioration of health status requiring discontinuation of treatment without objective evidence of disease progression at that time should be reported as "*symptomatic deterioration*." Every effort should be made to document the objective progression even after discontinuation of treatment.

For Patients with Non-Measurable Disease (i.e., Non-Target Disease)

Non-Target Lesions	New Lesions	Overall Response
CR	No	CR
Non-CR/non-PD	No	Non-CR/non-PD*
Not all evaluated	No	not evaluated
Unequivocal PD	Yes or No	PD
Any	Yes	PD

* 'Non-CR/non-PD' is preferred over 'stable disease' for non-target disease since SD is increasingly used as an endpoint for assessment of efficacy in some trials so to assign this category when no lesions can be measured is not advised

Duration of Response

Duration of overall response: The duration of overall response is measured from the time measurement criteria are met for CR or PR (whichever is first recorded) until the first date that recurrent or progressive disease is objectively documented (taking as reference for progressive disease the smallest measurements recorded since the treatment started).

The duration of overall CR is measured from the time measurement criteria are first met for CR until the first date that progressive disease is objectively documented.

Duration of stable disease: Stable disease is measured from the start of the treatment until the criteria for progression are met, taking as reference the smallest measurements recorded since the treatment started, including the baseline measurements.

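### The disease control rate is a stated secondary objective, but the planned medians and box-plots estimate no rate and make no allowance for censored response durations

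*Combined protocol and SAP*

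**What the plan says.** The objective in Section 1.2 is "To estimate the disease control rate, progression-free survival (PFS), and overall survival (OS) of exemestane for up to 1 year", counted from enrollment. The synopsis says the same. Both list the rate separately from PFS and OS.

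Section 12.2 has no disease control rate. What it lists is "Response duration, progression-free survival and survival will be assessed until 1 year after study enrollment", using the RECIST definitions in Appendix II.

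Section 13.1 gives the secondary endpoint as "disease-control as measured by response duration, progression-free and overall survival through 12 months from study enrollment".

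Section 13.3 names a proportion with a 95% confidence interval for the primary response endpoint, and proportions for toxicities. For time-to-event outcomes it says "The secondary endpoints of survival and progression-free survival will be estimated with Kaplan-Meier curves". The next sentence is "Disease control will be assessed with descriptive statistics and plots such as medians, ranges, interquartile ranges and box-plots".

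Under Section 6.5, patients who stop treatment without progression are "followed for disease response per standard of care until disease progression or the start of a new treatment, whichever is shorter", and all follow-up ends at 1 year.

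Appendix II states who is evaluable for response and defines CR, PR, SD, PD and best overall response. It measures duration of overall response from first CR or PR to documented progression, and defines duration of stable disease separately.

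**The concern.** A rate is a proportion: so many patients controlled, out of so many, at a stated time. Medians, quartiles and box-plots describe a continuous variable and cannot supply one. Followed literally, Section 13.3 would leave the Section 1.2 objective unanswered, or leave its time point and analysis set to be settled once the data are in hand.

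If disease control is instead taken as response duration, some durations will be incomplete, because assessment stops at new treatment and at 1 year. An ordinary median or box-plot must then either count an unfinished duration as finished or leave it out. Both errors run towards durations that are too short. The plan uses a censoring-aware method for PFS and survival, but not here.

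**Working it through.** The plan states no figure for disease control, so there is none to reproduce. The check has four parts.

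**1. Does any section specify the rate?**

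| Place | Disease control appears as | Method named |
|---|---|---|
| Synopsis, 1.2 | a rate | none |
| 12.2 | not listed; response duration is | none |
| 13.1 | response duration, or that with PFS and OS | none |
| 13.3 | disease control | medians, ranges, IQRs, box-plots |
| Appendix II | response categories, evaluable set, two durations | none |

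The components exist in Appendix II, but no section combines them into a rate with categories, a time point and an interval.

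**2. How many patients would response duration describe?** Section 13.2 gives response rates of 5% (null) and 20% (alternative), and the full sample is 29. Expected responders, ignoring selection at Stage 1: 29 × 0.05 = 1.45 and 29 × 0.20 = 5.8, so about 1 to 6 patients.

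**3. How much does censoring matter?** Assumptions, not in the plan: exponential durations with true median m months, response first seen at week 6, follow-up to week 52, no other censoring.

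- Observable time: 52 − 6 = 46 weeks; 46 / (52.18/12) = 10.58 months.
- Fraction censored: q = exp(−ln 2 × 10.58 / m).
- Median if unfinished durations count as finished: min(m, 10.58). Upper quartile: min(2m, 10.58).
- Median of completed durations only: −ln(1 − 0.5(1 − q)) × m / ln 2.

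| True median (months) | Censored | Median, counted as finished | Upper quartile, counted as finished (true) | Median, completed only |
|---|---|---|---|---|
| 3 | 8.7% | 3 | 6 (6) | 2.6 |
| 6 | 29% | 6 | 10.6 (12) | 3.8 |
| 9 | 44% | 9 | 10.6 (18) | 4.2 |
| 12 | 54% | 10.6 | 10.6 (24) | 4.5 |

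The ±7-day scan window changes 46 weeks to 45 or 47 and moves the censored fractions by less than one percentage point. A simulation in weeks agrees: for a true median of 12 weeks, 7% are censored, the median of all observed times is 11.9 and that of completed durations 10.8; for 26 weeks, 29% are censored and the completed-only median is 16.3.

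**4. What would the rate look like?** With an assumed 12 of 29 controlled, 12/29 = 41.4%, exact 95% CI 23.5% to 61.1%. Section 6.1 replaces patients who miss the first re-evaluation. If k such treated patients are counted as not controlled, the rate becomes 12/(29 + k): 40.0% for k = 1, 37.5% for k = 3, 34.3% for k = 6 (k assumed).

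The 6-week scan falls at 42 ± 7 days, that is 35 to 49 days after the start of treatment. Stable disease at that scan therefore meets the Appendix II requirement of more than 4 weeks (28 days) from baseline.

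**The case against.** The strongest defence is that the pieces are already there. Appendix II defines the response categories and who is evaluable, and the synopsis groups CR, PR and SD at 6 weeks when saying who may continue. The list in Section 13.3 is given as examples, so it does not rule out a proportion. Section 13.1 can be read as covering response duration, PFS and OS together, and Kaplan-Meier then covers two of the three.

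Part of this stands. It would be wrong to infer that the plan has no denominator: Appendix II supplies an evaluable set, and it includes patients who progress objectively before the end of cycle 1, which limits how far leaving out unevaluable patients can inflate a rate. It would also be wrong to infer that patients with stable disease contribute nothing to disease control. That follows only if disease control means duration of overall response alone, and Appendix II also defines a duration of stable disease.

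The defence does not close the gap. An open list of examples is not a specification, and Section 13.3 names proportions for response and toxicity but not here. The synopsis grouping is a rule for continuing treatment, not an endpoint. The wider reading of Section 13.1 still yields no rate and leaves response duration without a method that handles censoring.

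It is also fair that Kaplan-Meier on 1 to 6 responders will be imprecise. That limits what can be learned about duration, but does not justify treating unfinished durations as finished or dropping them.

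**Conclusion.** The mismatch is real and should be corrected before analysis. The objective is a rate; the planned summaries do not estimate one, and the plan does not say how the Appendix II definitions form the disease control endpoint.

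The censoring part depends on how long responses last. At a true median of about 3 months, the median and upper quartile are unbiased when all observed times are kept, and the completed-only median is slightly low (2.6 months). The problem becomes material for long responses: with 29% censored (true median 6 months) the upper quartile is cut from 12 to 10.6 months, and with 54% censored (true median 12 months) the median is capped as well. These are illustrations under exponential durations and response at week 6, not forecasts. A reader might infer that the reported durations are bound to be badly biased; the documents do not support that, since they give no expected duration and do not say how unfinished durations would be treated. The added effect of new treatment is not quantified, because the documents give no rate for it.

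One descriptive secondary endpoint is affected. The two-stage decision rule and the sample size rest on objective response and are untouched.

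**What to change.** Amend Sections 12.2, 13.1 and 13.3 together.

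1. List the disease control rate as a secondary endpoint and define it once: the proportion with CR, PR or SD at the 6-week re-evaluation. Report it with an exact 95% CI in the Appendix II evaluable patients. As a sensitivity analysis, report it in all treated patients, counting those without a re-evaluation as not controlled. Make clear in Section 1.2 that the 1-year horizon applies to PFS and OS.
2. List response duration as its own endpoint. Replace the medians and box-plots with Kaplan-Meier among responders, using the Appendix II start and end dates and censoring at the last disease assessment before new treatment or at 1 year. State how death without documented progression is handled, and note that the estimate will be imprecise with about 1 to 6 expected responders.

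The cost is a few sentences and a few lines of code. No new data are needed, because disease is already reassessed every 6 weeks.

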2.5 Rationale

While modest improvements have been made in survival and quality of life in patients with advanced non-small cell lung cancer (NSCLC) there is a need to explore new agents and combinations with novel mechanisms of action in an effort to improve clinical outcomes in this patient population. With the introduction of immune checkpoint blockade and the durability of response, the vast majority of patients with NSCLC are receiving immune checkpoint blockade at some point in their therapy. However, response rate is relatively low spawning interest in developing novel combination therapies that can improve upon the response or generate responses in patients who are failing therapy. It is generally accepted that the aromatase inhibitor (AI) exemestane is less toxic than chemotherapy, yet potentially it can provide equal or greater benefit. In hormone receptor positive breast cancer, anti-estrogen therapy is a first-line treatment for metastatic disease,

and is given as adjuvant therapy for 5 years in earlier stage disease. Exemestane has been used in tens of thousands of women and its efficacy and side effect profile has been well established. Furthermore, preclinical and clinical data suggest that there might be a role of estrogen receptor signaling in maintaining immune suppression in the tumor microenvironment. Therefore, we propose a 2-stage phase II trial of exemestane in previously treated postmenopausal women with metastatic NSCLC who are progressing on anti-PD1 or anti-PDL1 therapy to determine if aromatase inhibition will result in treatment responses in this patient population and to determine whether ER-related biomarkers can identify patients likely to receive clinical benefit.

The estrogen pathway inhibition is a promising novel target in NSCLC. Preclinical evidence support targeting the synthesis of estrogen in NSCLC as a strategy that may result in enhanced antitumor activity.

3 Study Design

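### Section 13.3 compares biomarkers by response only after cutting them in two; an exact rank test on the uncut value would usually have more power and costs only wording

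*Combined protocol and SAP*

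**What the plan says.** The method is in Section 13.3: "Biomarkers will be evaluated by evaluation of quartiles with subsequent dichotomization and then comparison by response using a Chi-square test". The stated alternative is Fisher's test, and the choice between the two is left to the sample size. It covers five tumor-tissue markers at baseline and six blood markers, the latter also at individual time-points after treatment starts. The section names no cut and no rule for choosing one. It plans no rank test and no model on the uncut value for the comparison by response. Repeated-measures analysis is mentioned only for change over time, and only if warranted.

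Section 13.3 describes the biomarker work as mainly descriptive, and Section 1.3 calls it exploratory. Section 13.3 also says the results will help set selection criteria for later studies, and Section 2.5 gives as one purpose of the trial "to determine whether ER-related biomarkers can identify patients likely to receive clinical benefit".

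The sample is fixed by Section 13.1: "an additional 19 patients will be enrolled in stage 2 for a total of 29 patients". The same section sets the success rule: "If the total number of patients responding is 4 or greater, the treatment will be considered worthy of further investigation".

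**The concern.** Cutting an ordered measurement into two groups discards the ordering within each group. With 29 patients and a handful of responders there is little information to spare. A single fixed cut is therefore likely to miss a marker that a rank test on the same data would detect. The 2x2 result also depends heavily on where the cut falls and on which side the middle patient is placed.

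At stake is what the trial passes on to later studies: which markers look worth carrying forward as selection criteria, and how strong the association appears. A rank-based estimate does not depend on a cut; the planned analysis does.

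**Working it through.** **The plan's own figure.** Section 13 gives no power, effect size or error rate for the biomarker comparisons. The only stated operating figures are those of the two-stage design in Section 13.2: 5% type I error and 80% power, for response rates of 5% and 20%. With a stage 1 threshold of g responses in 10 and success at 4 of 29:

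P(success) = Σ over x₁ ≥ g of b(x₁; 10, p) × P(Bin(19, p) ≥ 4 − x₁)

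- g = 2, as Section 13.1 is written ("If 2 or more patients have an objective response after completion of stage 1"): 0.026 at p = 0.05 and 0.596 at p = 0.20.
- g = 1: 0.047 and 0.801, which matches the stated 5% and 80%.

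So Section 13.2 does not reproduce under the written stage 1 rule, and the two sections must be reconciled. That is a separate matter. It enters here only through the number of responders.

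**Responders to expect.** At a 20% response rate, 0.20 × 29 = 5.8. Four is the minimum for a positive trial. I therefore looked at 3 to 8.

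**Assumptions, none of them in the documents.** Marker normal with SD 1; responders shifted up by 1 SD, which corresponds to an area under the ROC curve of Φ(1/√2) = 0.76; no missing values; two-sided tests at 5%. Median cut with 14 or 15 patients in the high group; upper quartile with 7. Best of three means the smallest Fisher p over cuts leaving 22, 14 or 7 patients in the high group. There were 100,000 simulated data sets per setting.

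| Responders | Exact rank test | Fisher, median, 14 high | Fisher, median, 15 high | Fisher, upper quartile | Fisher, best of three | False positives, best of three |
|---|---|---|---|---|---|---|
| 3 | 31% | 0% | 0% | 16% | 16% | 2% |
| 4 | 37% | 39% | 0% | 38% | 53% | 10% |
| 5 | 45% | 29% | 34% | 20% | 36% | 5% |
| 6 | 52% | 20% | 25% | 36% | 42% | 5% |
| 7 | 56% | 48% | 17% | 51% | 65% | 10% |
| 8 | 60% | 36% | 44% | 29% | 46% | 5% |

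The rank test's own false-positive rate is 4–5% throughout.

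**Why the median cut can have no power.** With 4 responders, all in a high group of 14, Fisher's p is C(14,4)/C(29,4) = 1001/23751 = 0.042. With 15 in the high group, the same perfect separation gives (1365 + 1001)/23751 = 0.0996, so an upward shift cannot reach 5%. With 3 responders and 14 high, the smallest upward p is C(14,3)/C(29,3) = 364/3654 = 0.0996, so the median cut fails on either side.

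**Sensitivity to effect size.** Responders drawn at a 20% rate, in trials with at least 2 responses in stage 1:

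| Shift (SD) | Exact rank test | Fisher, one fixed cut |
|---|---|---|
| 1.0 | 53% | 26–36% |
| 1.25 | 70% | 38–51% |
| 1.5 | 85% | 51–67% |

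In the same setting with no association, the rank test's error is 4.6%, Fisher's at one fixed cut is 2.0–2.9%, and Fisher's at the best of three cuts is 6.2%.

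**The case against.** The strongest reply is that the analysis is labelled exploratory, no decision in this trial rests on it, and later validation is foreseen. That stands, and it limits the weight of the point. Under the written stage 1 rule only 62% of trials reach 29 patients at a 20% response rate (1 − 0.8¹⁰ − 10 × 0.2 × 0.8⁹ = 0.624), and 9% do at 5%. In a trial that stops with one responder in 10, the rank test cannot reach 5% either (smallest two-sided p is 2/10 = 0.20).

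It is also fair that the plan never says the median. A well-placed cut can nearly match the rank test, as the upper quartile does at 4 and 7 responders. The tissue scoring scale is not given, and mutations are binary by nature, so the point does not reach every marker.

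Three stronger readings are tempting but unsupported:

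- **That looking at quartiles first inflates false positives.** Examining a marker's own distribution without reference to response inflates nothing. Inflation needs a cut chosen by its association with response. Section 13.3 puts the dichotomization before the comparison and does not describe such a choice; it merely fails to rule it out.
- **That low power and inflated error occur together in full.** The power loss belongs to a fixed cut, the inflation to a selected one. At 4 to 6 responders a selected cut recovers most of the power.
- **That the Chi-square error rates are the relevant ones.** The best of three cuts with an uncorrected Chi-square gives about 12% on average. But with 4 to 8 responders and a median split, the smallest expected count is only 4 × 14/29 = 1.9 to 8 × 14/29 = 3.9, and Section 13.3 lets sample size decide the test. Fisher's is the natural choice.

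**Conclusion.** The point holds as a minor one. For markers on a continuous or ordinal scale, the planned 2x2 comparison is usually weaker than an exact rank test on the same data. With a 1 SD shift the loss at one fixed cut is about 11 to 32 percentage points at 5, 6 or 8 responders (45 − 34 = 11; 52 − 20 = 32). At 7 responders it runs from 5 points (56 − 51) to 39 (56 − 17). At 4 it is nil, or total if 15 patients are in the high group at the median. Cut selection is an unclosed possibility rather than a stated practice. If it happened, Fisher's false-positive rate would be about 10% at 4 or 7 responders and close to nominal at 5, 6 and 8.

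These sizes rest on normality, the assumed shift and the group sizes used. The direction holds for every cut tabulated at 5 to 8 responders. That the markers are continuous or ordinal is inferred from the planned use of quartiles and from Section 9.2, which describes blood levels and immunohistochemistry. The primary endpoint and its decision rule are not affected.

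**What to change.** Amend Section 13.3 as follows:

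- For biomarkers measured on a continuous or ordinal scale, make an exact Wilcoxon rank-sum test on the uncut value the main comparison by response. Report the area under the ROC curve with a confidence interval.
- Keep quartiles as description.
- Label any dichotomized result exploratory. Choose the cut without regard to response, and state which group a value equal to the cut joins. Fixing the cut at the median in advance is not enough on its own, because of the all-or-nothing behavior at 4 responders.
- Keep Fisher's exact test for markers that are binary by nature, such as mutations.

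The cost is analysis wording only: no new data, samples, visits or patients.
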